3.1.2.3. Use of Antipyretic Medication

The use of antipyretic medication is also recorded in the e-diary from Day 1 through Day 7, where Day 1 is the day of vaccination. For the use of antipyretic medication from Day 1 through Day 7 after vaccination, the following endpoints and variables will be derived for analysis following the same rules as for local reactions (see [Section 3.1.2.1](#)) where applicable.

- Presence (yes or no) of use of antipyretic medication on each day (Day 1 through Day 7).
- Presence (yes or no) of use of antipyretic medication on any day (Day 1 through Day 7).
- Duration (first to last day reported) of use of antipyretic medication.
- Onset day of use of antipyretic medication.

The use of antipyretic medication will be summarized and included in the systemic event summary tables but will not be considered a systemic event.

3.1.2.4. Adverse Events

Standard algorithms for handling missing AE dates and missing AE severity will be applied as described in the Pfizer vaccine data standard rules. AEs will be collected from the time the participant provides informed consent through 4 weeks following vaccination.

Any AE reported in the CRF and considered as a reactogenicity event ([Section 3.1.2](#)) during clinical review and the data pooling process will not be included in any of the derivation included in [Section 3.1.2.4](#) and Section 3.1.2.5. However, if those reactogenicity AEs lead to discontinuation, or are immediate AEs, SAEs, or medically attended AEs, they will still be included in the AE data.

The following derivations will be included for each participant:

- Any AE reported.
- Any related AE reported.
- Any immediate AE (assess acute reactions for at least 30 minutes after study intervention administration).
- Any severe AE.
- Any life-threatening AE.
- Any AE leading to study withdrawal.
- Any AE leading to death.
- Any AESI.
 - A confirmed diagnosis of myocarditis or pericarditis.

The following analysis intervals will be defined for the above endpoints:

- From Day 1 (vaccination day) through 7 days after vaccination.
- From Day 8 through 4 weeks after vaccination (Visit 3).
- From Day 1 through 4 weeks after vaccination (Visit 3).

The analysis interval of “From 4 weeks after vaccination (Visit 3) through 6 months after vaccination (Visit 4)” will also be defined for endpoints of ‘Any AE leading to death’ and ‘Any AESI’.

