#### **8.3.4. Reactogenicity Electronic Diary (Reactogenicity Subset Participants Only)**

Participants in the reactogenicity subset will be required to complete a reactogenicity e-diary through an application installed on a provisioned device or on the participant's own personal device. These participants will be asked to monitor and record local reactions, systemic

events, and use of antipyretic medication for 7 days, where Day 1 is the day of study intervention administration.

The reactogenicity e-diary allows recording of these assessments only within a fixed time window, thus providing the accurate representation of the participant's experience at that time. Data on local reactions and systemic events reported in the reactogenicity e-diary will be transferred electronically to a third-party vendor, where they will be available for review by investigators and the Pfizer clinicians at all times via an internet-based portal.

At intervals agreed to by the vendor and Pfizer, these data will be transferred electronically into Pfizer's database for analysis and reporting. These data do not need to be reported by the investigator in the CRF.

Investigators (or a designee) will be required to review the reactogenicity e-diary data online at frequent intervals as part of the ongoing safety review.

The investigator or designee must obtain stop dates from the participant for any ongoing local reactions, systemic events, or use of antipyretic medication on the last day that the reactogenicity e-diary was completed. The stop dates should be documented in the source documents and the information entered in the CRF.

All other participants will not complete a reactogenicity e-diary but will have their local reactions and systemic events detected and reported as AEs in accordance with [Section 8.4.2](#).

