3.1.2. Primary Safety Endpoint

- Local reactions for up to 7 days following vaccination.
- Systemic events for up to 7 days following vaccination.
- AEs through 4 weeks after vaccination.
- SAEs through 6 months after vaccination.

It has been requested by the regulatory agency to combine reactogenicity data from different sources, such as the e-diary and AE CRF. Since the AE CRF does not designate a specific page to collect reactogenicity data that are missing from the e-diary, Pfizer has adopted a process of providing a listing of AEs reported within 7 days after vaccination to the clinical team to review/query the AEs and flag the preferred terms that should be considered as reactogenicity events before the database is locked. AEs reported on the same day of vaccination, but missing AE start times are defaulted to AEs after vaccination. Only those AEs reported within 7 days with completed AE start dates after vaccination, matched with the flagged preferred terms, will be pooled with reactogenicity data from the e-diary. If the same reactogenicity event is reported on the same day from both the e-diary and AE CRF, the highest grade from the 2 data sources will be used for that specific day.

It should be noted that the data collection in the AE CRF is different from that in the e-diary:

- For redness, swelling, and fever, the measured size and temperature are recorded in the e-diary, but not in the AE CRF. Therefore, the maximum grading for the 3 items reported in the e-diary will be based on actual size and FDA toxicity grading scale, but the maximum grading of the 3 reactogenicity terms from the AE CRF will be based on the grading scale in the CRF page. Across the 7 days, only the maximum grading from both sources will be used for the aggregated severity analysis, though the grading algorithm is different between the 2 data sources.
- For pain at the injection site and all systemic events, the severity grading algorithm in the e-diary and AE CRF may not be the same; the highest severity grade will be used.
- Both related and nonrelated solicited reactogenicity events that are recorded on the AE CRF will be included.

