- If a participant did not have any e-diary data transferred, the AE CRF data will not be used for derivation because the AE CRF is considered as “supplemental” for reactogenicity data missed on certain days but not all 7 days. In other words, if a participant did not report any e-diary data, the participant will not be included in the reactogenicity population.

Related and nonrelated reactogenic SAEs will be presented in both reactogenicity and AE tables. Immediate AEs and AEs leading to discontinuation, as well as reactogenicity AEs for participants not in the reactogenicity population, will be summarized with the AE tables.

In addition, a separate reactogenicity analysis will also be performed without combining any reactogenicity data collected from the AE CRF.

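### For non-serious Day 1 to 7 reactogenicity terms, the AE tables mix two definitions over one safety-population denominator, so these rates depend on the size of the e-diary subset

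*SAP*

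**What the plan says.** The AE estimand (Protocol 3; SAP 2.2.1) is the percentage of vaccinated participants reporting AEs through 4 weeks, under a treatment policy strategy. It makes no exception for reactogenicity events. SAP 6.1.3.1 analyses it in the whole safety population, by arm, for each age group and overall.

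What counts as an AE depends on whether the participant has e-diary data.

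- **Outside the reactogenicity population.** Protocol 8.3.4 says participants not in the subset "will have their local reactions and systemic events detected and reported as AEs in accordance with" the usual AE procedures. SAP 3.1.2 confirms that "reactogenicity AEs for participants not in the reactogenicity population, will be summarized with the AE tables".
- **Inside it.** Protocol 8.3.4 does not require diary reactions to be entered in the CRF, although 8.3.4.1 sends confirmed Grade 4 reactions to the AE log. For events that do reach the CRF, SAP 3.1.2.4 states: "Any AE reported in the CRF and considered as a reactogenicity event" during clinical review and pooling "will not be included in any of the derivation included in" the AE and SAE derivation sections. The exceptions follow: "if those reactogenicity AEs lead to discontinuation, or are immediate AEs, SAEs, or medically attended AEs, they will still be included".
- **Scope of the pooling.** SAP 3.1.2: "Only those AEs reported within 7 days with completed AE start dates after vaccination, matched with the flagged preferred terms, will be pooled" with the diary data. It also says: "If a participant did not have any e-diary data transferred, the AE CRF data will not be used for derivation".

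The wording of SAP 3.1.2.4 does not itself restrict the exclusion to participants with e-diary data. That restriction is found only in SAP 3.1.2, to which it cross-refers.

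**The concern.** A non-serious chill on Day 2 counts as an AE for a participant outside the subset. Inside the subset it normally does not count, either because it was recorded only in the diary or because the CRF entry was flagged and removed. Both participants are in the same denominator. For these terms the displayed rate describes neither all AEs nor unsolicited AEs.

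Three uses of the tables are affected:

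- The size of the Tier 1 and Tier 2 between-arm differences (SAP 6.6.1) depends on the subset share.
- Tier 2 status is set by a term's incidence in any group (SAP 3.5.1; the threshold is redacted). A flagged term could fall below it on the mixed rate and lose its confidence interval.
- The subset is sized within each age stratum, and a second season may add a further subset (SAP 2.3). If the share differs by stratum or season, comparisons between strata and the combined summary for ages 18 and over mix in different proportions.

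Nothing planned separates the two definitions. The supplementary AE analyses (SAP 6.1.3.2) and subset analyses (SAP 6.4) include neither a split by reactogenicity-population status nor a single-definition analysis. The comparison of e-diary-only with combined data (SAP 3.1.2 and 6.6.1) concerns the solicited-event tables.

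**Working it through.** **The plan's own figure.** The only numeric safety sizing is Protocol Table 7, the probability of at least one AE, 1 − (1 − p)^N. At p = 0.01% this gives 0.2592 for N = 3,000, 0.8364 for N = 18,100 and 0.9008 for N = 23,100. The table shows 0.26, 0.84 and 0.90. It reproduces and is not in dispute. The documents give no figure for the effect examined here.

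**Inputs, all assumed.**

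- s, the share of the safety population in the reactogenicity population: 0.1 to 0.5, because subset and stratum sizes are redacted.
- u, the rate of other AEs: 10% in both arms.
- r, the rate of CRF-recorded reactogenicity AEs outside the subset: 15% for qIRV, 5% for QIV.
- u and r act independently, s is the same in both arms, and exempt events inside the subset are ignored.

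**Any-AE rate as planned.** P = s·u + (1 − s)(u + r − u·r), which simplifies to u + (1 − s)(1 − u)r. With equal u, the arm difference is (1 − s)(1 − u)(r_qIRV − r_QIV). If everyone's reactions counted, it would be (1 − u)(r_qIRV − r_QIV). The ratio is 1 − s.

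| Definition | qIRV | QIV | Difference (points) |
|---|---|---|---|
| Counted for everyone | 23.5% | 14.5% | 9.0 |
| As planned, s = 0.1 | 22.15% | 14.05% | 8.1 |
| As planned, s = 0.2 | 20.8% | 13.6% | 7.2 |
| As planned, s = 0.5 | 16.75% | 12.25% | 4.5 |
| Counted for no one | 10% | 10% | 0 |

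Only the reactogenicity component shrinks by 1 − s. The whole any-AE rate shrinks less: at s = 0.2 the qIRV rate falls from 23.5% to 20.8%, or 2.7/23.5 = 11%.

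**A single flagged term.** The pooled difference is (1 − s) times the difference outside the subset. With an assumed 10% versus 4% (6.0 points), it is 5.4 points at s = 0.10, 4.8 at 0.20 and 3.9 at 0.35.

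**How much comes from the SAP removal rule alone.** If a fraction q of e-diary participants have a flagged, non-exempt CRF event, removing it lowers the any-AE rate by s·q·(1 − u). With q = 1% (assumed), that is 0.1 × 0.01 × 0.9 = 0.09 points at s = 0.1 and 0.45 points at s = 0.5. The total qIRV gaps from the table are 23.5 − 22.15 = 1.35 and 23.5 − 16.75 = 6.75 points. Under these assumptions the removal rule accounts for one fifteenth of the gap. The rest arises because diary reactions do not become CRF AEs.

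**The case against.** The strongest reply is that the AE tables are not where these terms are judged. Local reactions and systemic events are primary safety endpoints in their own right, solicited daily and analysed in the e-diary population (SAP 6.1.2.1). Pooling the two sources was a regulatory request (SAP 3.1.2), and removing pooled events from the AE tables limits double counting. Primary safety is descriptive, SAP 6.6.1 calls the tiered analysis exploratory, and no interval is specified for an arm difference in any AE. If subset membership is balanced across arms, mixing alters the size of a term's difference, not its sign. SAP 3.1.2 also says openly where the non-subset events go.

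All of this stands, and it limits the consequence. It does not make the pooled AE rates interpretable for the affected terms.

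A reader might also infer four stronger things that the documents do not support:

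- **That the SAP rule is the main cause.** Protocol 8.3.4 keeps most diary reactions out of the CRF, so the rule has little to remove.
- **That subset participants cannot contribute to these terms.** The four exceptions stay in. So do events after Day 7 and events with incomplete start dates, which are never pooled.
- **That AE rates are simply diluted.** This holds against an all-AE definition. Against unsolicited AEs only, the planned rate is inflated (20.8% against 10% in the example at s = 0.2).
- **That an overall table of all CRF-reported AEs would cure it.** Such a table would still lack diary-only reactions and remain a mixture.

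**Conclusion.** The point holds for non-serious flagged terms on Days 1 to 7 and for the Day 1 to 4-week total that includes them. Their AE rates and Tier 1/2 differences depend on the share of participants in the reactogenicity population. Relative to an all-AE definition, which is how the estimand is worded, the reactogenicity component falls to about 1 − s of its size: 0.90 to 0.50 for s of 0.1 to 0.5. SAEs and AEs from Day 8 to 4 weeks are not affected.

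The factor assumes balanced subset membership, equal background AE rates in the arms, and that subset reactions would otherwise have been recorded as they are outside it. The actual size cannot be computed because the subset and stratum numbers are redacted. No hypothesis test depends on it. This is an inexpensive improvement in interpretability; the documents do not support reading it as a concealed safety difference.

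**What to change.** 1. In SAP 6.1.3 and 6.6.1, present the AE tables, including Tier 1 and Tier 2 differences, separately for participants in and not in the reactogenicity e-diary population. This is the main remedy.
2. Add one supplementary analysis that applies a single definition to everyone. One option is to exclude flagged Day 1 to 7 terms for all participants, with the same exceptions and the same start-date rule throughout.
3. Label the pooled table as combining two AE definitions, and report the subset share by arm and age stratum beside it.
4. Reconcile SAP 3.1.2.4 with SAP 3.1.2 by stating in 3.1.2.4 whether its exclusion applies only to participants with e-diary data. Programmed from its own wording alone, it could remove flagged events for everyone and produce materially different tables.

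The data are already due to be collected, and the efficacy and immunogenicity analyses are untouched. The cost is a longer set of AE tables.

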3.1.2.5. Serious Adverse Events

SAEs will be collected from the time the participant provides informed consent to approximately 6 months after vaccination.

The following analysis intervals will be defined for SAEs:

- From Day 1 (vaccination day) through 7 days after vaccination.

- From Day 8 through 4 weeks after vaccination (Visit 3).
- From 4 weeks after vaccination (Visit 3) through 6 months after vaccination (Visit 4).
- From Day 1 through 4 weeks after vaccination (Visit 3).
- From Day 1 through 6 months after vaccination (Visit 4).

3.2. Secondary Endpoint(s)

3.2.1. Secondary Immunogenicity Endpoints (CCI)

- HAI titers for each strain at baseline and 4 weeks after vaccination.
- Presence of HAI seroconversion for each strain at baseline and 4 weeks after vaccination.
- HAI titer fold rise for each strain from before vaccination to 4 weeks after vaccination.
- Presence of HAI titers $\geq 1:40$ for each strain before vaccination and at 4 weeks after vaccination.

3.2.2. Secondary Efficacy Endpoints

- First-episode LCI cases with associated per-protocol ILI, caused by any strain, in each age population.
- First-episode LCI cases with associated per-protocol ILI, caused by all matched strains.
- First-episode LCI cases with associated per-protocol ILI, caused each matched strain.
- First-episode LCI cases with associated per-protocol ILI, caused all unmatched strains.
- First-episode CCI cases with associated per-protocol ILI, caused by any strain.
- First-episode LCI cases associated with ILI, as defined by applying a modified CDC definition, caused by any strain.
- First-episode LCI cases associated with ILI, as defined by applying the WHO definition, caused by any strain.
- First-episode cases of influenza, as confirmed by central or local RT-PCR or culture, with associated per-protocol ILI.

[figure not shown]
A vaccine-matched (antigenically similar) strain is defined as a CCI relative to a reference serum. This analysis is conducted as part of the AMT, conducted at a central laboratory, and will be used for antigenic characterization of influenza viruses recovered in cultured samples to determine if they are matched strains to the vaccine, as stated “matched strains” in the above efficacy endpoints. Some examples of

matched/unmatched strains for A/B strains, based on PCR laboratory and culture results, are in the table below.

Strain	Confirmed PP ILI PCR+	AMT A/CCI	AMT A/CCI
Matched A/CCI	POS	POS	NEG
Matched A/CCI	POS	NEG	POS
Unmatched A	POS	NEG	NEG
Strain	Confirmed PP ILI PCR+	AMT B/CCI	AMT B/CCI
Matched B/CCI	POS	POS	NEG
Matched A/CCI	POS	NEG	POS
Unmatched B	POS	NEG	NEG

3.3. Other/Exploratory Endpoint(s)

CCI

3.4. Baseline Variables

Unless otherwise specified, the last nonmissing measurements or samples collected prior to vaccination are considered the baseline data for the assessments.

3.4.1. Demographics and Medical History

The demographic variables are age at vaccination (in years), sex (male or female), race (Black/African American, American Indian, or Alaskan native, Asian, Native Hawaiian or other Pacific Islander, White, not reported), ethnicity (Hispanic/Latino/of Spanish origin, non-Hispanic/non-Latino/not of Spanish origin, not reported), and racial designation (Japanese, other). In cases where more than 1 category is selected for race, the participant would be counted under the category “multiracial” for analysis. BMI will also be included in the demographic variables.

Age at the time of vaccination (in years) will be derived based on the participant’s birthday. For example, if the vaccination day is 1 day before the participant’s 19th birthday, the participant is 18 years old. For participants who were randomized but not vaccinated, the randomization date will be used in place of the date of vaccination for the age calculation. If the randomization date is also missing, then the informed consent date will be used for the age calculation.

Medical history will be categorized according to MedDRA.

3.4.2. E-Diary Completion

An e-diary will be considered transmitted if any data for the 3 local reactions (redness, swelling, pain at the injection site), 7 systemic events (vomiting, diarrhea, headache, fatigue, chills, new or worsening muscle pain, and new or worsening joint pain) and fever, or use of antipyretic/pain medication to treat symptoms, are present on any day. If all data are missing for all items on the e-diary for all 7 days after vaccination, then the e-diary will be considered not transmitted.

An e-diary will be considered completed if all expected data for all 7 days are available (ie, not missing). Otherwise, the e-diary will be considered incomplete. For any given day, an e-diary will be considered complete if all expected data are available.

For transmitted e-diaries, the following variables will be defined: “Day 1,” “Day 2,” “Day 3,” “Day 4,” “Day 5,” “Day 6,” and “Day 7.”

For completed e-diaries, the following variables will be defined: “Day 1,” “Day 2,” “Day 3,” “Day 4,” “Day 5,” “Day 6,” “Day 7,” and “Day 1 through Day 7.”

“Day 1-Day 7” is the variable for participants who completed e-diaries on all 7 days.

3.4.3. Prior/Concomitant Vaccines and Concomitant Medications

The name and date of administration for any concomitant medications and nonstudy vaccinations received from 28 days prior to study enrollment until the last visit (Visit 4) will be collected and recorded in the CRF. Details of concomitant medications and vaccination will be recorded in the CRF, and concomitant medications used to treat ILI symptoms will be collected in the ILI CRF.

The following concomitant medications and vaccinations will be recorded in the CRF:

- Prior receipt of any COVID-19 vaccine.
- Prior receipt of any pneumococcal vaccine.
- Licensed influenza vaccine, if received within the 12 months prior to enrollment.
- Any vaccinations received from 28 days prior to study enrollment until the last visit (Visit 4).
- Prohibited medications listed in [Section 6.9.1 of the protocol](#), if taken, will be recorded and include start and stop dates, name of the medication, dose, unit, route, and frequency.

Nonstudy vaccines and concomitant medications will be coded using the WHODD.

3.5. Safety Endpoints

Local reaction, systemic event, AE, AESI, and SAE assessments have been described above in the primary safety endpoints.

3.5.1. Adverse Events

A 3-tier approach will be used to summarize AEs. Under this approach, AEs are classified into 1 of 3 tiers. Different analyses will be performed for different tiers (refer to [Section 6.6.1](#)).

- Tier 1 events: These are prespecified events of clinical importance and are maintained in a list in the product's safety review plan.
- Tier 2 events: These are events that are not Tier 1 but are “common.” A MedDRA PT is defined as a Tier 2 event if its incidence is at [CCI](#) in any study intervention group.
- Tier 3 events: These are events that are neither Tier 1 nor Tier 2 events.

3.5.2. Physical Examinations, Including Vital Signs

Physical examination findings collected during the study will be considered source data and will not be required to be reported. Any untoward physical examination findings that are identified during the active collection period and meet the definition of an AE or SAE will be recorded in the CRF.

The participant's oral temperature will be measured prior to vaccination. Weight and height will also be measured prior to vaccination. Any untoward vital sign findings that are identified during the active collection period and meet the definition of an AE or SAE will be recorded in the CRF.

3.5.3. Laboratory Data

Clinical safety laboratory assessments will not be collected in this study.

